#### **8.5 Sample Storage Procedures**

The samples will be stored in pseudo-anonymised form with the participant's trial ID written on the label in a local hospital freezer at an optimal temperature for the troponin assay until collection. The samples should be put in the freezer within two hours of preparation. The samples will not be destroyed if a patient withdraws from the study unless they specifically request so. If the patient requests for the samples to be destroyed the Tissue Custodian (Chief Investigator), will inform the lab who will ensure the samples are destructed as per the Human Tissue Act. This will be documented in the TMF and ISF of the participating site.

#### 8.6 Sample and result recording and reporting

Troponin-T will be measured by the Doctors Laboratory and shared with the Chief Investigator by secure electronic communication after the last patient sample has been analysed.

#### 8.7 Sample management at end of study

The samples will be stored beyond the end of the trial to be used for closely related studies in the future. After completion of any potential sub-studies the samples will be destroyed according to the Human Tissue Authority's Code of Practice.

[figure not shown]
#### 9.0 Investigational Device

#### 9.1 Name and description of Investigational Device

A full description of the investigational device AffeX-CT to be used is provided in Investigator Brochure version 1.

The device is manufactured using standard electronic components, pbc assembly processes and ABS (Acrylonitrile butadiene styrene) for the casing, plus ear-clips comprised of moulded plastic parts with conductive rubber electrodes. Ear-clips are the only parts of the device that will be in contact with human aurciular tissue. *The AffeX* device is a hand-held, battery (9V) operated, portable device consisting of a signal-generating, amplifying electronics, control dials for patients to adjust the stimulation intensity. A pair of stimulation electrodes in the form of ear-clips are used to apply the electrical signal to the skin (stimulation surface) of the tragi bilaterally. *AffeX* device produces a fixed electric current signal consisting of 30 Hz biphasic asymmetrical pulses with 200 µs duration of the positive phase. The current waveform has an adjustable amplitude of between 0 and 80 mA. Usually, the stimulation is applied with the intensity between 1-4 mA. The signal is transmitted through the skin of the tragus to the subcutaneous nerves. Each stimulation is designed to be applied for at least 60 min daily.

#### 9.2 Intended Performance

Investigation Brochure appendix B details Instructions for Use of the investigational device. AffeX-CT has been set to deliver a biphasic pulse with the following parameters: The performance of each device has been validated to meet the Intended Performance specification.

# **Waveform parameters:**

- Channel: Dual, isolated between channels
- Mode of operation: continuous,
- Pulse intensity: recommended range for the investigation is 0.1-8mA (device range is 0-80mA)
- Pulse Rate: 30 Hz
- Pulse width: 200 μsec
- Duration /Time: Continuous for 30min
- Wave Form: Bi-Phasic Asymmetrical square pulse
- Electrical specification:
- Battery 9v (6F22)
- Mechanical specification:
- Dimensions: 95(H) x 60(W) x 23(T) mm

NHS Trust

Weight: 115 grams (inc. battery)

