#### 6.7 Trial intervention

Each participant will have the Affex-CT device connected to both ears via electrical leads. The device will be preset to deliver either transcutaneous autonomic neuromodulation or no stimulation. In the treatment arm, the device will be turned 'On' by a trained member of the research team and the transcutaneous autonomic neuromodulation will be applied continuously until the end of the stimulation period when the device will be turned 'Off'. For the control arm, no stimulation will be applied.

The intervention will be administered across two time points in each participant. The first will be delivered for the entire duration of the mechanical thrombectomy procedure. The start of mechanical thrombectomy is defined at induction of anaesthesia which is the patient's arrival in the anaesthetic room but before being wheeled into the radiology suite. The end of mechanical thrombectomy is defined as the point the patient leaves the radiology suite to be taken to the post recovery anaesthetic room. The second will be delivered on the morning after mechanical thrombectomy regardless of the time when the first procedure was administered. This will happen typically in the morning between 0800-1200h for one hour (± 10 minutes). The duration of participation is seven days from the start of the mechanical thrombectomy procedure for each participant. No special dietary or 'life-style' requirements will be imposed (this study will gather efficacy data for the intervention while establishing the feasibility of a full-scale trial).

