# 10.10 Usage schedules

- First administration will be for duration of mechanical thrombectomy [which typically lasts two hours]
- Second administration will be the morning after the mechanical thrombectomy [0800-1200h] which typically lasts one hour.
- No changes to usage schedule are required for different age groups or demographics.

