	 Exclusion criteria participation in a trial exploring similar biological mechanism; previous enrolment; anatomical contraindication (local ear abnormalities); pregnancy.
Interventions	Active stimulation bilateral active transauricular nerve stimulation for the duration of the mechanical thrombectomy procedure (AffeX-CT/001 investigational device). The intervention will be repeated for 1h the morning following the mechanical thrombectomy
	Sham stimulation bilateral sham transauricular nerve stimulation for the duration of the mechanical thrombectomy procedure (AffeX-CT/001 investigational device). The intervention will be repeated for 1h the morning following the mechanical thrombectomy
Primary outcome measure	The primary outcome is Blood pressure variability [Time Frame: 0-24h after mechanical thrombectomy], as calculated from the coefficient of variation of systolic blood pressure

3. Outcome measures

Primary outcome measure

The primary outcome is Blood pressure variability [Time Frame: 0-24h after mechanical thrombectomy], as reflected by the coefficient of variation of systolic blood pressure.

Secondary outcome measures

- 1. Systolic and diastolic blood pressure variability in the first 24h after mechanical thrombectomy [Time Frame: 0-24h after mechanical thrombectomy]: systolic and diastolic blood pressure mean, standard deviation, and coefficient of variation.
- 2. Heart rate variability [Time Frame: 0-24h after mechanical thrombectomy]: time and frequency domain measures of autonomic cardiac modulation.
- 3. NIH Stroke Scale (NIHSS) [Time Frame: recorded before, at 24h after mechanical thrombectomy]
- 4. Organ dysfunction [Time Frame: First seven days after mechanical thrombectomy.] defined as clinical need for intravenous pharmacological support for blood pressure [pressors or intravenous antihypertensive medication]; arrythmias; myocardial injury [high sensitivity troponin]; hospital-acquired infection.

Exposure variables

The exposure is bilateral active or sham transauricular nerve stimulation for the duration of the mechanical thrombectomy procedure (AffeX-CT/001 investigational device), an intervention that is be repeated for 1h the morning following the mechanical thrombectomy (provided the patient remains in Royal London Hospital).

Sample size and randomisation

Sample size calculation

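### Protocol section 9.2 gives the trial device a 30-minute duration, which contradicts section 9.1 and the treatment schedule in the protocol and SAP

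*Protocol*

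**What the plan says.** Protocol section 9.2 introduces its parameter list with "AffeX-CT has been set to deliver a biphasic pulse with the following parameters" and adds: "The performance of each device has been validated to meet the Intended Performance specification". Under Waveform parameters, the list contains "Duration /Time: Continuous for 30min".

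The other statements of session length are longer:

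- Section 9.1: "Each stimulation is designed to be applied for at least 60 min daily".
- Section 6.7, first session: "The first will be delivered for the entire duration of the mechanical thrombectomy procedure". Section 10.10 gives its usual length: "First administration will be for duration of mechanical thrombectomy [which typically lasts two hours".
- Section 6.7, second session: "between 0800-1200h for one hour (± 10 minutes".
- SAP section 2, Interventions: stimulation for the duration of the procedure, and then "The intervention will be repeated for 1h the morning following the mechanical thrombectomy".

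The protocol also describes the end of a session in two ways. In section 6.7 a trained team member turns the device on and it is turned off when the stimulation period ends; Appendix A has the research team doing both. In section 10.8 the device runs for a fixed time, with no value given, and then stops by itself.

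**The concern.** Session length is part of the dose. An entry in the device performance specification that is shorter than every scheduled session cannot be right alongside that schedule, and nothing in the protocol or SAP confines the 30 minutes to a bench test, explains it or provides for restarting the device. The automatic stop in section 10.8 makes the entry more than cosmetic, because 30 minutes is the only fixed device duration that the protocol states.

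If the devices did cut off at 30 minutes, the active arm would receive a fraction of the intended stimulation. Staff might not see this at the bedside: the thrombectomy is done under general anaesthesia or sedation (section 5.1), the current is set one division below the level that causes tingling (section 10.8), and the staff on and off times could still span the full session. For a pilot meant to inform a larger trial, it would then be hard to say what dose a positive or a null result relates to.

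**Working it through.** The plan has no calculated figure to reproduce here. The check compares the stated durations and then works out what a real cut-off would mean.

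**Step 1. Durations side by side**

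| Source | Stated length |
|---|---|
| Protocol 9.2 | 30 min |
| Protocol 9.1 | at least 60 min |
| Protocol 6.7 and 10.10, session 1 | whole procedure, typically 120 min |
| Protocol 6.7, session 2 | 60 ± 10 min, so 50 to 70 min |
| SAP section 2, session 2 | 60 min |

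Thirty minutes is below every other entry, including the 50-minute lower limit for session 2. Against section 9.1 it is 30/60 = 50%.

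**Step 2. Does the synopsis settle it?** It gives roughly 1 to 3 hours of treatment in total. Two 30-minute runs make 2 × 30 = 60 min = 1 h; the typical schedule makes 120 + 60 = 180 min = 3 h. Both readings fit, so it does not.

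**Step 3. Share delivered, on condition that a 30-minute timer runs once per session with no restart**

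- Session 1: 30/120 = 25%. For assumed procedures of 60 to 180 min (the documents give only the typical two hours): 30/60 = 50% down to 30/180 = 17%.
- Session 2: 30/60 = 50%. Over the permitted window: 30/50 = 60% down to 30/70 = 43%.
- Both sessions: 60/(120 + 60) = 33%. Over the session 2 window: 60/170 = 35% down to 60/190 = 32%. For assumed procedures of 60 to 180 min: 60/120 = 50% down to 60/240 = 25%.

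**Step 4. The other branch.** With no timer the loss is about zero. With a timer and prompt restarts it is also about zero: 120/30 − 1 = 3 restarts in a typical session 1 and 60/30 − 1 = 1 in session 2.

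**Step 5. Would a short session be recorded?**

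- Sections 6.9 and 10.5 say that the device stores its own usage.
- Section 10.11 makes an incomplete session a protocol deviation. Its instruction to reattach covers a patient who stops the device or takes off the clips, not a timeout.
- The SAP section on protocol deviations reports, per group, the number of patients with at least one deviation of any kind, with no threshold. SAP Table 3 also counts deviations with no threshold. The 5% rule governs only separate listing: 0.05 × 36 = 1.8, so two patients are enough.
- Table 3 has no row for minutes delivered, so the planned tables would show that sessions were short but not by how much.

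**Step 6. Sample size.** The stated inputs (coefficient of variation 15 against 10, SD 4, 90% power, 5% level, 5% non-compliance per group) include no session length. The figure of 36 does not depend on this point.

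**The case against.** The strongest reply is that nobody would dose from this line. The list in section 9.2 mixes settings with a recommended intensity range, battery type, dimensions and weight, and nothing in it calls 30 minutes a cut-off. How long staff should stimulate is stated consistently in sections 6.1, 6.7 and 10.10 and in the SAP. The automatic stop in section 10.8 is tied to the end of the stimulation period, so it is not in itself a contradiction. The entry may be left over from the 30-minute work in trauma patients mentioned in the Introduction. The Investigator Brochure, which holds the full device description and the instructions for use, may settle the matter and was not available here.

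Most of this stands, and it limits the point. A reader might infer that patients will receive only 30 minutes per session; the documents do not show that any 30-minute timer operates. A reader might also infer that a shortfall would go unrecorded. The device log and the deviation counts would hold it, and the argument from anaesthesia concerns the thrombectomy, not the session next morning.

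What does not stand is that the entry can be left alone. Section 9.2 says that the devices were set and validated to these values, and a left-over figure there is still a wrong figure. If the Brochure gives the right one, the protocol should agree with it.

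**Conclusion.** The inconsistency is certain: 30 minutes in section 9.2 conflicts with section 9.1 and with the schedule in sections 6.7 and 10.10 and the SAP, and the fixed run time in section 10.8 fits neither a procedure of variable length nor the switch-off by staff. Under-delivery is conditional. The figures of 25%, 50% and 33% assume a working 30-minute timer, one run per session, no restart, a two-hour procedure and a 60-minute second session; without the timer, or with restarts, the loss is about zero.

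A loss of power is a further tempting inference. The documents give no relation between minutes of stimulation and blood pressure variability, so none can be claimed. Endpoints, analysis and N = 36 are unaffected. This is a minor to moderate document correction, and would become more serious only if a 30-minute timer were confirmed.

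**What to change.** 1. **Establish the facts first.** The manufacturer confirms, from the Investigator Brochure or device testing, whether any automatic cut-off exists and that the devices can run for the whole procedure and for 60 ± 10 min. It already programs the devices (section 6.3), is unblinded (6.4) and tests each one before delivery (10.1). Section 6.3 shows programming for allocation only, so it should not be assumed that duration can be reset. The answer should be one pooled statement, with no setting listed by device number, so that allocation is not revealed.
2. **Then correct the text.** Change the duration entry in section 9.2 to match sections 6.7 and 10.10. In section 10.8, replace the fixed run time and automatic stop with switch-off by staff at the end of the period. If a timer cannot be removed, state its length and add to section 10.11 a rule that staff restart the device at each timeout until the session is complete.
3. **Optional, and not needed for the correction.** Add a row for minutes delivered per session to the SAP Table 3 shell before unblinding, and fill it from the device log after data lock. The row must not first be added after unblinding, since the SAP's remit is to fix analyses in advance.

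The cost is one manufacturer confirmation covering 36 + 12 = 48 devices plus reserves of unstated number, within a testing duty that already exists, and a few wording edits. Visits and blinding do not change.

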### 10.0 Legal status of Investigational Device

AffeX-CT device has not been approved by the MHRA for use as "a non-implanted, non-invasive transcutaneous autonomic neuromodulation device for the functional management of the arterial blood pressure" (Intended Use).

It has been supplied for 'research only' use as "a non-implanted, non-invasive transcutaneous autonomic neuromodulation device for the functional management of the arterial blood pressure" (Intended Use). The AffeX-CT device is a TENS device (Totally TENS, model WL-2103A/TT-21AL) on which it is based has been marketed as an Over-The-Counter (OTC) TENS device (Intended Use: (with a clinical prescription) for the symptomatic relief and management of chronic (long term) pain. No adverse events have been reported.

The trial device falls within the European Medical Device Regulations (MDR) as a Class IIa device in line with other TENS devices and Class II device by the FDA. The AffeX-CT device uses the Totally TENS, model WL-2103A/TT-21AL product which has been designed and manufactured to ISO13485 Quality Management System. The device is manufactured using standard electronic components, pcb assembly processes and ABS (Acrylonitrile butadiene styrene) for the casing. Ear-clips use moulded plastic parts with conductive silicone rubber electrodes. Each device is designed for use by one participant only and must not be re-used by other participants. There will be in total 36 individual investigational devices supplied for the trial, one for each participant and 12 devices as replacements devices should devices issued to participant fail or malfunction. Each device is marked with a unique identification number. The electrodes supplied with the device will also be marked with the device's unique identification number. Additional devices will be supplied for training purposes and in reserve, if any participants encounter issues or cases of malfunction.

The device is compliant with the following electrical, mechanical and safety standards: Mechanical:

- Robustness EN 60601-1 (Classification IP22)
- Water resistance EN60529 (Classification IP22)
- Ingres protection EN60529 (Classification IP22)

#### Electrical:

- EMC susceptibility / immunity IEC 60601-1-2/60601-1-2
- Low voltage safety IEC 60601-1-2/60601-1-2
- Quality Management System used: ISO 13485: 2016

#### 10.1 Device Manufacturer(s) and supply arrangements

For the purpose of the VANS study, the AffeX-CT device is being used 'off-label' and Afferent Medical Solutions Ltd will assume responsibilities of 'the manufacturer' and must therefore fulfil all the requirements of a manufacturer as set out in the UK Medical Devices Regulations 2002, including notification of a clinical investigation to the MHRA.

Named supplier (Afferent Medical Solutions) ("Afferent") will assume responsibility for:

- manufacturing
- labelling in accordance with the medical device's regulations 2002, ISO14155 and GCP
- separately testing and calibrating each device prior to the delivery to the trial team
- delivering the investigational units to the research facility
- assuming management of and providing maintenance services
- each device will have a unique identification number which will appear on the device labels.
   Their associated ear-clip & leads and carry case will also have an identification label with the same identification number as the device

All devise deficacy and event reporting to the MHRA

- disposal of devices

The Sponsor will be responsible for the management of collecting all units upon trial completion and their return to Afferent Medical Solutions (see CIP section 10.9 destruction, return, and recall devices). An approved courier service will transport the investigational devices to Royal London Hospital. A log recording receipt of the medical devices will be kept. Devices will be returned to the manufacturer at the end of the trial by courier.

#### **10.2 Investigational Device Accessories**

AffeX-CT is a standalone device and supplied as following:

- Control Unit
- 4x Ear-clips and connecting leads
- Battery (6F22)
- User Guide
- Instructions for Use (IFU) (see Investigator Brochure appendix B)

NHS
Barts Health
NHS Trust

- Storage case (soft bag)

#### 10.3 Packaging and labelling of Investigational Devices

The devices will be packaged and labelled in accordance with the Medical Devices Regulations 2002 and ISO14155 GCP. No special requirements for this non-sterile product are necessary.

Each device will have the following labels on the front cover:

# Front cover of device **VANS** clinicaltrials.gov No: NCT05417009 **EXCLUSIVELY FOR CLINICAL INVESTIGATIONS** Keep out of the reach and sight of children AffeX-CT Treatment Code: Serial Number: Investigator: [name] Sponsor: Queen Mary University of London, [name] [contact] Max Setting Max Setting Patient ID RIGHT Back cover of device Afferent Medical Solutions Ltd Exclusively for clinical investigation [name] **[name]**

Refer to Investigator Brochure appendix A for more information on Symbols and Nomenclature Description. The carry case will have the information appearing on the front cover label printed on it. AffeX-CT is a non-sterile product.

There are no special requirements for packaging. Device will be labelled in accordance with medical device regulations 2002 and ISO 14155 GCP (see Investigator Brochure 10.5; appendix E). Front labels are to be colour coded; range of colours for participants and white labelled for demonstration/training devices.

The ear-clips will be colour coded, white and black and red and black to allow users to identify which ear-clip should be attached to the left and right ear.

#### 10.4 Accountability and Traceability

Each investigational device will be assigned a unique identification number. The Chief Investigator and investigator sites will maintain accountability logs at sites and delivery records to record the dates when:

- devices were received, the name of the person who received them and the quantity received
- each device was used, who used it and the trial identifier of the participant it was used on.
- devices were returned including the name of the person who returned or disposed of the device.
- any devices were returned because they were unused, expired or malfunctioning. Lot numbers, batch numbers and/or serial numbers will be used to trace devices.

#### 10.5 Assessment of compliance

Each investigational device monitors and records delivery of programmed current, thus storing usage information internally. Treatment non-compliance will be documented by the investigator and reported to the Sponsor. There is no minimum compliance threshold. All non-compliant participants are followed up.

#### **10.6** Device storage

Each investigational devices will be stored in a locked cupboard within the Critical Care and Perioperative Medicine research group secure storage site. Devices held at the research site must be stored in a secure location (e.g., locked cupboard), with access limited strictly to members of the investigation team.

Only members of the investigation teams will have access to the investigational devices. No special storage requirements are necessary for the device.

After use, participants will be urged to unplug the ear clip leads from the unit, and place all components back into the sachet/casing, in such a way, as to minimise the chance of accidental removal or damage (e.g., drawer or shelf)

# 10.7 Device training and experience requirements

Prior to the trial start, a training session will be conducted by an Afferent trainer for members of the Investigation site team. In case of any additional inquiries, contact details to a delegated Afferent representative, as well as the trainer, will be provided, to respond to any requests and for provision of any additional information. Investigation site team will be responsible for training participants in the use of the device. They will also be required to follow a set training routine, which will include an assessment of the participant's ability to satisfactorily use the device. This will be documented on a training log.

